Official Title: Aspirin as Adjuvant Therapy in Young Psychotic Patients NCT number: NCT02685748

Study Protocol and Statistical Analysis Plan

Effect of adjuvant aspirin therapy on neurological soft signs and PANSS in young psychotic patients

A randomized, interventional, double-blind, placebo-controlled clinical trial

Protocol name:	Aspirin2016.2
Date:	25 October 2016.
Donor:	Stanley Medical Research Institute, [name], [name] 20815, SAD
Sponsor:	Clinic for Mental Diseases "[name]", [name], Serbia
Principal Investigator, Grant Holder:	MD [name], psychiatrist
Co-investigators:	MD/PhD [name], neuropsychiatrist MD [name], psychiatrist MD [name], psychiatrist

Background:

The clinical trial team would conduct a randomized, interventional, double-blind, placebo-controlled study in two parallel groups of patients who were neuroleptically naive or previously minimally medicated (who did not take antipsychotics during the previous 6 months) with the illness duration of up to seven years. Patients of both sexes, ages 18 to 28, would participate in the trial, in accordance with the tenth revision of the International Classification of Diseases (ICD10), they would meet the diagnostic criteria for the illnesses ranging from F 20 to F 29. After meeting the inclusion and exclusion criteria and having signed an informed consent form, the patients would be randomized into two groups:

Experimental group - EG: antipsychotic + Aspirin

and

Control group – CG: antipsychotic + placebo.

The EG patients would be administered 1000 mg aspirin pro die with gastric protection pantoprazole 40 mg pro die, both medicines in two doses during 6 weeks of hospital treatment at Clinic form Mental Disorders "[name]". The trial would last for 18 months and would include the total of 100 to 120 patients.

Objective and hypotheses:

The objective of the trial would be to determine the effect of adjuvant aspirin therapy on neurological soft signs, positive and negative syndrome in schizophrenia, cognition, inflammatory factors and cytokine profile.

Working hypotheses:

- 1. Changes in PANSS and MoCA scores as well as inflammation factors in both patient groups, more in the experimental group.
- 2. Changes in the cytokine profile in both patient groups.

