Three visits are planned. The first visit after admission to the Clinic. If the patient fulfils the inclusion criteria and none of the exclusion criteria (anamnestic data, somatic and psychiatric examination), and after the Informed consent form has been signed, PANSS scale test and blood sample would be taken for laboratory analysis. Laboratory analysis would be complete blood count (RBC, WBC, PTC, Hgb, Hct), sedimentation, C reactive protein, blood biochemical analysis (glycaemia, cholesterol, triglycerides, transaminases, CK, bilirubin, uric acid, creatinine, urea), and electrolytes (Na, K). Th1, Th2 and Th17 cytokines would be subject to the immunological assays. Each patient would be given an identification number (from one upwards) and the tubes with serum for the cytokine profile would be labelled with the same number, in terms of x/y, where x is the patient's identification number and y- may be "1" or "2" ("a" or "b"), where "1" or "a" would mean the first blood draw (at the beginning of the trial) and the number "2" or "b" - the second blood draw (at the very end of the trial).

After calming down of the acute signs of psychosis, between the third and fifth day of hospitalization, the second visit would be made when testing of the neurological soft signs would be performed according the Heidelberg Soft Neurological Signs Scale, the MoCA Cognitive Assessment Scale, and then the patient would be randomized to an experimental or control group if he/she meets the inclusion and no-exclusion criteria, if there are no somatic contraindications (with a stable ECG), and if he/she still wishes to participate in the trial.

The staff of the ward where the patient would be accommodated would be given two boxes of medicines labelled "Clinical Trial Medication 1" and "Clinical Trial Medication 2" that would be administered to patients – one medicine from each box, in the morning and in the evening.

After 6 weeks from the second visit (+/- 3 days), the third visit would be made when the patient would be examined, the PANSS, MoCA and Heidelberg scales testing repeated, and the blood sample taken again for laboratory analyses - inflammatory factors and cytokine profiles.

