Control laboratory analyses would be performed on each patient on days 14th and 28th from the second visit. If patients received high dose valproic acid in therapy, valproatemia control would be performed, and if they received antidepressants from the SSRI group, bleeding time would be controlled.

Serums administered to patients would be transported in a cold chain to the Centre for Molecular Medicine and Stem Cell Research at the Faculty of Medical Sciences, University of Kragujevac, where they would be stored at -70°C until analyses were performed.

Criteria for Trial Termination:

The criteria for trial termination for individual subjects, parts of the trial or the whole trial would be defined as follows: the subject may voluntarily leave the trial at any moment. In the event that side effects of adjuvant aspirin therapy occur, the patient would be excluded from the trial. Occurrence of bleeding from the nose or gums, bruising, bleeding in the GIT or brain, and confusion, anaphylactic reactions or acute renal failure would imply the immediate exclusion of subjects from the trial. If there is an increase in valproatemia (in patients taking valproic acid in therapy) - the dose of the medicine would be excluded from the trial. The entire trial would be discontinued by the emergence of a large number of complicated side effects, as well as by compromising drug storage.

Selection and inclusion of subjects:

Inclusion criteria:

- Age 18 to 28
- Diagnostic categories from F 20 to F 29
- Illness duration \leq 7 years

> Exclusion criteria:

- PAS abuse
- Primary cognitive impairment
- Contraindications and special caution for acetylsalicylic acid and pantoprazole:
 - Hypersensitivity to acetylsalicylic acid and other NSAIDs (possible cross-reaction)
 - Gastric ulcer and/or duodenum ulcer, gastritis
 - Pregnancy
 - Haemophilia, bleeding disorders
 - Gout

- Asthma, COPD, NSAID-induced bronchospasm
- Angioedema, urticaria
- Haemolytic anaemia
- Use of warfarin, methotrexate
- Diabetes
- Decreased liver and / or kidney function
- Heart failure
- Surgical/dental intervention
- Interactions with specific psycho-pharmaceuticals
- Sensitivity to pantoprazole

Statistical analysis plan:

Statistical data analysis will be done in the programme IBM SPSS Statistics v.20.

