Continuous variables will be displayed descriptively using the minimum and maximum values, mean values and standard deviation. Categorical variables will be presented descriptively using absolute and relative frequency as well as graphically using a pie chart.

Kolmogorov-Smirnov or Shapiro-Wilk test, depending on sample size, will be used to check the normality of data distribution, as well as graphical method of using histogram. If the data follow the normal distribution, parametric tests will be used for the statistical analysis of the data; otherwise the corresponding non-parametric tests will be used.

For the analysis of significant continuous variables over time, the Paired Samples t Test will be used if the data follow a normal distribution or the Wilcoxon test if the data do not follow the normal distribution. Significant results will be presented graphically using a bar chart or boxplot.

For the analysis of significant difference of continuous variables between the control and experimental groups, the Independent Samples t Test will be used if the data follow a normal distribution or the Mann-Whitney test if the data do not follow the normal distribution. Significant results will be presented graphically using a bar chart or boxplot.

For the analysis of the dependence between two continuous variables, the value of Pearson's or Spirman's correlation coefficient will be interpreted. In the case of strong correlations, the dependence will be shown both by the regression equation and graphically using the scatterplot.

For the analysis of the dependence between the two categorical variables, a Chi-squared test, that is, a Fisher's exact-dependency test will be used. The results will be presented graphically using a bar cluster graph.

The results will be considered statistically significant if the p value is less than 0.05.

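### The plan does not say what the day 14 and 28 blood analyses contain or whether they enter the CRP and ESR analysis, and the SAP has no baseline adjustment

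*Combined protocol and SAP*

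**What the plan says.** Under Objective and hypotheses, inflammatory factors are part of the objective. Hypothesis 1 expects them to change in both groups, and more so on aspirin.

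Clinical Trial Design gives three sets of blood work:

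- **Visit 1.** "Laboratory analysis would be complete blood count (RBC, WBC, PTC, Hgb, Hct), sedimentation, C reactive protein", followed by biochemistry and electrolytes. This is the only panel the document itemises.
- **Days 14 and 28.** "Control laboratory analyses would be performed on each patient on days 14th and 28th from the second visit". No analytes are listed. The next sentence concerns valproate levels and bleeding time in patients on particular co-medication.
- **Visit 3, six weeks (±3 days) after visit 2.** "the blood sample taken again for laboratory analyses - inflammatory factors and cytokine profiles".

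Cytokine serum is drawn twice only, at the start and then at "the second blood draw (at the very end of the trial".

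The Statistical analysis plan provides the following for continuous outcomes: "For the analysis of significant continuous variables over time, the Paired Samples t Test will be used if the data follow a normal distribution", with Wilcoxon as the alternative, and an independent-samples t test or Mann-Whitney test between groups. It does not say which visits, or which summary of them, enter any test. It contains no covariate adjustment, no repeated-measures model and no rule for patients without a visit 3 value. The threshold is a p value below 0.05.

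**The concern.** CRP and ESR may exist at four times per patient: visit 1, days 14 and 28, and about day 42. The SAP's methods take two time points, or one value per patient, at a time, and nothing says whether the two middle values count. Three things are at stake.

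- **Precision.** A comparison that ignores baseline, and possibly the interim values, is less precise than it need be.
- **Early leavers.** Criteria for Trial Termination lets patients leave at any time and removes those with aspirin side effects. Such a patient may have a day 14 or day 28 value but no visit 3 value. Removal for aspirin side effects could also differ between arms.
- **Choice of contrast.** With visits unspecified, several comparisons could be run, each at the same 0.05 threshold, and none is named as the one that decides.

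**Working it through.** The documents state no effect size, SD, within-patient correlation, dropout rate or power, so there is no figure of the plan's own to reproduce. What follows is an illustration under stated assumptions.

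**Inputs from the documents.** Total sample size: "would include the total of 100 to 120 patients". Significance: "The results will be considered statistically significant if the p value is less than 0.05". On-treatment days: 14, 28 and about 42.

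**Assumptions.** Two-sided test; 1:1 allocation, so 50 to 60 per arm; no losses; CRP and ESR measured on all three on-treatment days; the same SD (set to 1) and the same correlation r between any two values; a difference of 0.3 SD at week 6.

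**Variance per patient**

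- Week-6 value, unadjusted: 1
- Week-6 value, baseline-adjusted: 1 − r²
- Mean of three on-treatment values, baseline-adjusted: (1 + 2r)/3 − r²

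| r | adjusted week 6 | adjusted three-day mean | ratio |
|---|---|---|---|
| 0.3 | 1 − 0.09 = 0.910 | 0.533 − 0.090 = 0.443 | 0.49 |
| 0.5 | 1 − 0.25 = 0.750 | 0.667 − 0.250 = 0.417 | 0.56 |
| 0.7 | 1 − 0.49 = 0.510 | 0.800 − 0.490 = 0.310 | 0.61 |

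**Power.** Two-sample t test with standardised effect d/√variance, at 50 / 60 per arm. In the constant case d = 0.3 on every day. In the linear case the effect is 0.1, 0.2 and 0.3 SD on days 14, 28 and 42, so the average is (0.1 + 0.2 + 0.3)/3 = 0.2 SD.

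| r | adjusted week 6 | three-day mean, constant effect | three-day mean, linear build-up |
|---|---|---|---|
| 0.3 | 34 / 40% | 61 / 69% | 32 / 37% |
| 0.5 | 40 / 47% | 63 / 71% | 34 / 39% |
| 0.7 | 55 / 63% | 76 / 83% | 43 / 50% |

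An unadjusted week-6 t test has 32 / 37% at every r.

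**Break-even.** The average beats adjusted week 6 only if the average effect exceeds √ratio times the week-6 effect: √0.49 = 0.70, √0.56 = 0.75 and √0.61 = 0.78 for r = 0.3, 0.5 and 0.7. Linear build-up gives 0.2/0.3 = 0.67, which falls short each time.

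**What the week-6 contrast itself gains.** Baseline adjustment alone takes its variance from 1 to 0.91, 0.75 or 0.51. With complete data, a repeated-measures model with unrestricted covariance and visit-specific baseline effects gives essentially the same week-6 contrast as ANCOVA. The interim values help that contrast mainly by keeping patients with no visit 3 value in the analysis. With no dropout figure, that part cannot be sized.

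**The case against.** The strongest reply is that the premise is not in the text. The day 14 and 28 analyses are called control analyses. They sit beside valproate and bleeding-time checks and just before the bleeding and renal exclusion rules. After visit 1, inflammatory factors are named only at visit 3. If the panel is for safety, no CRP or ESR value is being discarded, and leaving safety bloods out of an efficacy analysis is a legitimate choice. This stands, and it is why the point is conditional.

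A reader might go further and infer that the SAP's tests cannot use the interim values, so that CRP and ESR effects will be judged on one noisy week-6 value. The documents do not support that:

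- The listed tests could be run at any visit, on any pair of visits, or on a per-patient mean. The SAP does not specify which.
- A visit 1 value exists, the paired test uses two values, and the between-group test could be on change.
- No SD or correlation is given, so nothing shows the week-6 value to be noisy.
- Nor do the documents say that early leavers contribute nothing. No analysis set or missing-data rule is defined, and treatment is given in hospital, which may limit losses.

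It is also tempting to make the three-day average the deciding test. The linear case shows that this can lose power, so it is a trade-off and not a clear improvement.

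Finally, the scope is narrow. It covers CRP and ESR only, and the trial's title names soft signs and PANSS.

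What the reply does not remove is that the panel's content, the visits analysed and the handling of early leavers are all unstated, and baseline adjustment is absent even if the panel is safety-only.

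**Conclusion.** This is a specification gap with a minor to moderate efficiency cost, not an error that invalidates the inflammation analysis. A plain comparison at week 6 with the tests named remains valid.

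The certain part is that the interim results have no stated role and that no baseline adjustment is planned. Any loss of on-treatment values depends on CRP and ESR being in the control panel, which the documents neither state nor exclude.

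The size also depends on assumptions the documents cannot settle. With equal correlation of 0.3 to 0.7 and a constant effect from day 14, the averaged contrast has 49% to 61% of the variance of the adjusted week-6 value. With linear build-up to 0.3 SD, it has lower power than week 6 at each correlation examined. The conclusion does not extend to cytokines, which have no interim draw.

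**What to change.** 1. In Clinical Trial Design, list the day 14 and 28 analytes and say whether CRP and ESR are among them.
2. If they are, analyse log CRP and log ESR each with one baseline-adjusted repeated-measures model over the available on-treatment days, including every randomised patient with at least one on-treatment value. Name the week-6 difference between aspirin and placebo as the deciding contrast, and the average over days 14 to 42 as supportive.
3. If the control panel is safety-only, say so, and compare the arms at week 6 by ANCOVA with the visit 1 value as covariate.

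The cost is a few lines of protocol and SAP text and one mixed model or ANCOVA per marker, both available in SPSS. No extra blood draw is needed. Fixing the deciding contrast in advance also prevents a choice among visits after the data are seen.

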- 3. In case of significant change of SNS and cytokine profile in the experimental group the results would support the cytokine hypothesis. If there were no significant changes in the SNS in the experimental group, the results would support the SNS as a trait of schizophrenia.

Clinical Trial Design:

A randomized, interventional, double-blind, placebo-controlled clinical trial in two parallel groups of patients who were neuroleptically naive or previously minimally medicated (who did not take antipsychotics during the previous 6 months) with the illness duration of up to seven years. Patients of both sexes, ages 18 to 28, would participate in the trial, in accordance with the tenth revision of the International Classification of Diseases, would meet the diagnostic criteria for the illnesses ranging from F20 to F29. Upon fulfilment of inclusion and exclusion criteria and signed Informed consent form, they would be randomized in two groups: experimental (EG) and control group (CG). Patients belonging to the control group would be administered antipsychotic therapy and placebo, whereas patients in the experimental group would be administered regular antipsychotic therapy and aspirin. EG patients would be administered 1000 mg aspirin pro die with gastric protection- pantoprazole 40 mg pro die, both medicines in two doses in duration of 6 weeks.

A software application specialized in the randomization of subjects for clinical trials -*Sealed Envelope* - will be used for randomization. The obtained list will be in possession of one co-investigator and only he or she will know which group the patient belongs to. Only upon completion of the trial, after taking the serum samples from the last patient, and cytokine profile analysis (cytokine profile analysis would be performed at the end of the trial, after the serum sample from the last patient was taken at both test times) would the patient's belonging to the EG or CG group be revealed.

The co-investigator in charge of randomization would give out the medicine boxes and the medicines would all look identical - packed in the same capsules for overcapsulation by the company **Capsugel**. Placebo tablets would be manufactured by Galenika A.D. The patient would be administered Bayer's Aspirin tbl. á 500 mg and Nolpaza tbl. á 20 mg produced by Krka-Farma D.O.O.

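### Patients with aspirin side effects leave the trial after randomisation, with no stated follow-up or analysis set, so 6-week outcomes may be lost unequally by arm

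*Combined protocol and SAP*

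**What the plan says.** - **Timing of randomisation.** Clinical Trial Design places it at the second visit, after the Heidelberg and MoCA tests: "and then the patient would be randomized to an experimental or control group". Exclusions for side effects of study medication therefore come after randomisation.
- **Exclusion rule.** Criteria for Trial Termination states: "In the event that side effects of adjuvant aspirin therapy occur, the patient would be excluded from the trial". A list of events that includes nose or gum bleeding and bruising "would imply the immediate exclusion of subjects from the trial".
- **Uneven wording.** Two sentences after the side-effect rule, for raised valproate levels, a similar phrase is attached to a drug: "the dose of the medicine would be excluded from the trial". The section should use one term for leaving the trial and another for stopping a medicine.
- **Outcome visit.** At the third visit, 6 weeks (+/- 3 days) after the second, the plan has "the PANSS, MoCA and Heidelberg scales testing repeated, and the blood sample taken again for laboratory analyses". In between there are only safety bloods: "Control laboratory analyses would be performed on each patient on days 14th and 28th from the second visit".
- **Analysis.** The statistical analysis plan lists paired and independent t tests with their rank-based alternatives, correlations, and chi-squared or Fisher tests. It names no analysis population and no way of handling missing values.

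**The concern.** The trigger for exclusion is a side effect of aspirin, and only one arm receives aspirin. Blinding does not remove the asymmetry, because a rule applied identically in both arms takes out more patients where the drug causes the events. If those patients then have no 6-week visit, loss of outcome depends on the assigned treatment. The remaining groups are then no longer the randomised ones.

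Two analyses are exposed:

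- **The between-arm comparison.** It is biased if exclusion is unequal and the excluded patients would have had different outcomes.
- **The within-group comparison over time.** Hypothesis 3 turns on change in soft signs and cytokines within the experimental group. The paired test there is affected by selection in that group alone, and balanced losses in the control group do not cancel it.

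**Working it through.** The plan has no figure to reproduce: the total of 100 to 120 comes without an effect size, SD, power or dropout rate. What follows is illustration under assumptions.

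**Inputs**
- From the documents: 100 to 120 patients (Background), two arms, significance at p < 0.05.
- Assumed: 1:1 allocation (50 to 60 per arm), two-sided testing, no true aspirin effect, and SD 1 among patients of the same type.
- Also assumed, since the documents give none: exclusion proportions pE (experimental) and pC (control), and an outcome gap d in SD between excluded-type and other patients.

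**Between-arm bias.** Suppose a share pE of patients in each arm is of a type with outcomes shifted by d. All of them are excluded in the experimental arm, and a fraction pC/pE of them in the control arm. Experimental completers then have mean 0. Control completers still contain a share (pE − pC)/(1 − pC) of the shifted type. Hence

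bias = d (pE − pC)/(1 − pC).

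- 10%/5%, d = 0.5: 0.5 × 0.05/0.95 = 0.026 SD.
- 20%/5%, d = 1: 1 × 0.15/0.95 = 0.158 SD.

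Simulated two-sided error of the pooled t test (40,000 trials per cell):

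| Exclusion, experimental/control | Gap | Bias (SD) | Error, 50 / 60 per arm |
|---|---|---|---|
| 5%/2% | 0.5 | 0.015 | 5.2% / 5.1% |
| 10%/5% | 0.5 | 0.026 | 5.0% / 5.1% |
| 10%/5% | 1.0 | 0.053 | 5.7% / 5.8% |
| 15%/5% | 1.0 | 0.105 | 7.5% / 7.9% |
| 20%/5% | 0.5 | 0.079 | 6.5% / 6.8% |
| 20%/5% | 1.0 | 0.158 | 10.4% / 11.9% |

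Hand check of the last row at 50 per arm: 40 and 47.5 remain, so SE = √(1/40 + 1/47.5) = 0.215 and bias/SE = 0.74. The normal rejection probability is about 11%, in line with the table. With control exclusion at 5%, error passes 7.5% only at about 14% experimental exclusion (gap 1 SD) or 23 to 24% (gap 0.5 SD). The sign of d, and so of the bias, is not fixed by the documents.

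**Paired test in the experimental group.** Completers' mean change differs from that of the whole group by pE × d: 0.10 × 0.5 = 0.05 SD, or 0.20 × 1 = 0.20 SD at the extreme. For scale, the effect detectable with 80% power is 0.37 to 0.40 SD paired and 0.52 to 0.57 SD between arms.

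**What follow-up buys.** If 75% of excluded patients, chosen without regard to outcome, attend the 6-week visit in the 20%/5%, 1 SD case, the unobserved shares fall to 5% and 1.25%. The shifted type then makes up 0.15/0.95 = 0.158 of observed experimental patients and 0.1875/0.9875 = 0.190 of observed controls. The bias drops from 0.158 to 0.032 SD.

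**The case against.** Three objections carry weight.

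1. **The chain is conditional at each step.** It needs exclusion to mean no 6-week visit, unequal exclusion by arm, and a link between exclusion and outcome. A reader might infer that the plan withholds the final visit from excluded patients, but no sentence says so. A reader might also infer that the result will be biased, but nothing in the documents ties bruising or bleeding to PANSS, cognition, soft signs or cytokines. The model above is close to an upper case, since every exclusion comes from the shifted type. This stands, and it limits the severity.

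2. **High exclusion rates are less likely here.** The eligibility list screens out "Contraindications and special caution for acetylsalicylic acid and pantoprazole", the experimental group receives gastric protection, patients are 18 to 28, and exposure lasts 6 weeks. This also stands.

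3. **The matter is not wholly uncheckable afterwards.** PANSS and blood are taken at the first visit, and Heidelberg and MoCA before randomisation. Once the list is opened, exclusion counts by arm and baseline profiles of excluded and retained patients can be compared. It would be too strong to say that the trial could never examine the problem. What cannot be recovered is the missing 6-week values.

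Blinding is a weaker defence. Of the co-investigator who holds the list, the protocol says "only he or she will know which group the patient belongs to". That tells us who knows the allocation, not who decides on exclusion, and it does not make drug-caused events equal. The arms are defined by randomisation and no crossover is described, so the practical gap is missing outcomes, not patients analysed in the wrong arm.

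**Conclusion.** The point holds as a gap with a plausible route to bias. The plan removes patients after randomisation for a reason linked to one arm's drug, does not say that follow-up continues, has one outcome visit, and names no analysis set or missing-data rule.

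The documents do not support a claim that bias is present or large. Under the assumed inputs it is negligible at 10%/5% exclusion with a 0.5 SD gap, and material only when exclusions are frequent, unequal and strongly related to outcome. If exclusions are few, balanced or unrelated to outcome, the between-arm comparison is essentially unaffected.

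The case for acting rests on low cost and on data that cannot be collected later. I rate it a cheap improvement of modest severity.

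**What to change.** Leave the clinical triggers, and what they mean for study medication, as the sponsor sets them. Reconcile the wording of Criteria for Trial Termination so that leaving the trial and stopping a medicine are distinct. Then add:

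1. **Follow-up.** A side effect or listed event does not end follow-up. The third-visit PANSS, MoCA, Heidelberg and blood sample are still sought at 6 weeks (+/- 3 days) unless consent is withdrawn or assessment is not feasible.
2. **Primary analysis.** All randomised patients with third-visit data, in the arm assigned. An on-treatment analysis is secondary and labelled as a selected group.
3. **Reporting.** Exclusions and reasons by arm, with baseline values of excluded and retained patients.
4. **Sensitivity analysis for values still missing.** Multiple imputation by arm that includes the patient's own baseline value and pools the variance across imputations. Skewed cytokines are transformed or handled by a suitable method. Shifts applied by arm show where the conclusion changes. A single random draw should not be used: with 20%/5% missing and no bias at all, it gave a type I error of about 8% in simulation.

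**Cost.** Amendment wording and some follow-up effort. The assessments are already scheduled and treatment is planned as 6 weeks in hospital, so some patients may still be on site, though serious events may prevent testing. The as-randomised effect is also diluted. If those who stop gain nothing, the effect is multiplied by (1 − pE), for example 0.566 × 0.90 = 0.509 SD at 50 per arm. Power then falls from 80% with none stopping to about 76%, 71% and 61% at 5%, 10% and 20% stopping.

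### CRP, ESR and cytokines are trial objectives, but acute infection, inflammatory disease and anti-inflammatory drug use are neither excluded nor recorded; within-arm marker changes become uninterpretable and the between-arm comparison loses precision

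*Combined protocol and SAP*

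**What the plan says.** Under Objective and hypotheses, the trial aims to measure the effect of aspirin on, among other things, "cognition, inflammatory factors and cytokine profile". Working hypothesis 1 predicts "Changes in PANSS and MoCA scores as well as inflammation factors in both patient groups, more in the experimental group". Working hypothesis 3 takes significant change in soft signs and cytokines within the experimental group as support for the cytokine hypothesis.

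Under Clinical Trial Design, the first-visit blood sample covers "sedimentation, C reactive protein", a blood count including WBC, and Th1, Th2 and Th17 cytokines. Inflammatory factors and cytokines are sampled again at the third visit, six weeks after the second.

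Under Exclusion criteria, most items stand below the line "Contraindications and special caution for acetylsalicylic acid and pantoprazole". Substance abuse (as I read the abbreviation PAS) and "Primary cognitive impairment" are separate items. The only drugs named as excluded are in the item "Use of warfarin, methotrexate". NSAIDs appear only through hypersensitivity and bronchospasm. The only prior-medication window anywhere is for antipsychotics: patients "who did not take antipsychotics during the previous 6 months".

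The Statistical analysis plan provides paired t or Wilcoxon tests over time, and independent t or Mann-Whitney tests between groups, the choice depending on normality. It states no baseline adjustment.

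**The concern.** CRP, ESR and cytokines respond to infection, to inflammatory disease and to anti-inflammatory drugs. A patient admitted with a respiratory infection meets no named exclusion. If the infection clears, the markers fall by week 6 whichever capsule the patient receives. A patient taking an NSAID at entry starts from a baseline that the drug may already have lowered.

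Three uses of the data are affected:

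- **Within-arm tests.** The part of hypothesis 1 about change in both groups, and hypothesis 3, can be satisfied by resolving infection alone. Randomization does not protect a paired test inside one arm.
- **Between-arm tests on change.** A few large falls unrelated to treatment inflate the variance and can hide an aspirin effect.
- **Drug use during follow-up.** Anti-inflammatory treatment of control patients in the six weeks would shrink the contrast, and without a record nobody could tell afterwards.

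**Working it through.** The documents give no SD, effect size, power or infection rate for any marker, so there is no figure to reproduce. The calculation below is an illustration.

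**Inputs from the documents.** Total 100 to 120 patients; significance at p below 0.05; switch to rank tests when data are not normal.

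**Assumptions.** Equal allocation (50 to 60 per arm); two-sided testing; arms compared on change from baseline; SD of CRP change 5 mg/L without infection; a share f of each arm infected at admission, with an extra fall of 40 mg/L by week 6.

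**1. Spread of change scores.** SD = √(5² + f(1−f)·40²).

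- f = 5%: √(25 + 76) = 10.0; variance ratio 101/25 = 4.0
- f = 10%: √(25 + 144) = 13.0; ratio 169/25 = 6.8
- f = 15%: √(25 + 229 − 25) = √229 = 15.1; ratio 229/25 = 9.2

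These ratios are sample-size multipliers for a t-test on change. They are not the cost under this plan, because the distribution would be visibly non-normal. In simulation with 55 per arm, Shapiro-Wilk rejected normality in at least one arm in over 99% of trials at f = 5% and in all of them at 10% and 15%. The plan would then use Mann-Whitney.

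**2. Power between arms.** The effect is set to give about 80% power by t-test without infection: d = (1.960 + 0.842)·√(2/n) = 0.56 SD at n = 50, which is 0.56 × 5 = 2.8 mg/L. Simulated power at 50 per arm:

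| Infected share | Mann-Whitney | t-test |
|---|---|---|
| 0% | 78% | about 80% |
| 5% | 68% | 30% |
| 10% | 59% | 19% |
| 15% | 51% | 16% |

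At 55 per arm the Mann-Whitney figures are 68%, 60% and 53%. Restoring 80% with the rank test takes about 1.3 times the patients at 5% infected and 1.65 times at 10%.

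**3. Bias between arms.** With no aspirin effect, the rank test under these assumptions rejects in about 5% of trials. A separate simulation with milder falls (1 to 3 SD of change, f up to 20%, t-test) gave 4.8% to 5.6%. There is no systematic bias from baseline infection. The chance difference in infected share between arms has SD √(2f(1−f)/n): 4 percentage points at f = 5% with n = 60, and 8 points at f = 20% with n = 50.

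**4. Within-arm tests.** With no aspirin effect, 50 per arm and the assumptions above, the Wilcoxon test in the aspirin arm is significant in 9%, 21% and 39% of trials at f = 5%, 10% and 15% (paired t: 20%, 58%, 86%). With the milder falls, the paired t-test gives 6% to 13% at f = 5% and 25% to 78% at f = 20%.

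**5. Drug use in controls.** If a share p of controls takes an equally active anti-inflammatory through follow-up, a true difference Δ becomes Δ(1−p). The documents give no basis for p.

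**The case against.** **The list does more than screen for aspirin safety.** A reader might infer that it does only that. It does not: substance abuse and primary cognitive impairment are separate items. Gout, gastritis, asthma, COPD, diabetes, methotrexate and surgical or dental intervention also remove some inflammatory states, whatever the motive. Before randomization, patients must also be free of somatic contraindications, and this could stop someone overtly ill. That stands in part. But the check is undefined, is tied to the ECG and does not address drug use.

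**Randomization deals with it.** For bias between arms this is correct. A reader might infer that a difference between arms could be infection and not aspirin; the design does not support that, because infection at admission and prior drug use come before allocation. The comparative half of hypothesis 1 stays valid. What remains is lost precision.

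**The loss depends on choices the plan leaves open.** The plan does not say whether arms are compared on change or on week-6 values. On week-6 values, an infection that has cleared adds almost no variance and the illustrated loss largely disappears. The infection rate and size of fall are assumed. This stands, and is why the figures are a range under assumptions.

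**Excluding infected patients does not rescue within-arm inference.** Both arms start antipsychotic treatment in acute psychosis, so a change within one arm could not be credited to aspirin even in a clean sample. This also stands, and the fix addresses it.

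**Dilution by drug use is speculative.** These are inpatients, and nothing shows that controls would take anti-inflammatory drugs for six weeks. Agreed; the point is only that such use would go unrecorded.

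**Conclusion.** The omission is real. Inflammatory markers are objectives, yet no criterion excludes, and no section records, acute infection, autoimmune or chronic inflammatory disease in general, or use of NSAIDs, non-study aspirin, corticosteroids or immunomodulators other than methotrexate. The consequences are:

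- **Within arms:** marker changes cannot be attributed to aspirin, and infection makes spurious significance more likely.
- **Between arms:** no systematic bias from baseline infection, but a loss of power if change scores are used, from about 80% to roughly 68% to 51%. This rests on 5% to 15% infected, a 40 mg/L fall, an SD of 5 mg/L and 50 to 60 per arm.

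A reader might infer from the variance ratios that four to nine times as many patients are needed. That holds only for a t-test on change, which the plan's own normality rule would set aside. PANSS and soft signs, the outcomes named in the trial's title, are not touched by this argument. It is a worthwhile, inexpensive improvement to the marker objectives and not a flaw in the trial as a whole.

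**What to change.** **Exclusion criteria.** Add:

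- clinical acute infection or fever at visit 1;
- known autoimmune or chronic inflammatory disease;
- use of NSAIDs, non-study aspirin, corticosteroids or immunomodulators at the first blood draw or within a window before it that the protocol states in advance.

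Judge these from history and examination. Do not screen on CRP, ESR or WBC without a defined threshold: that could remove the inflamed patients in whom the hypothesis is of most interest.

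**Data collection.** Record infection and use of these drugs at each blood draw.

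**Statistical analysis plan.** Base conclusions about aspirin and the markers on the comparison between arms adjusted for baseline, for example ANCOVA on log values, and keep the paired tests descriptive. Pre-specify one sensitivity analysis that leaves out patients with infection or such drug use at baseline. Report infections and drug use after randomization descriptively or as sensitivity only, because the study drug may itself influence them.

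**Cost.** A protocol amendment, one extra case report form item, one sensitivity analysis and slightly slower recruitment. No new test or staff.
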